## I. The point of enrolment

Potential subjects are identified by the Investigator or study staff based on patients' clinical and radiographic assessments during regular medical care.

The point of enrolment could be during the preoperative visit, or even earlier. The enrolment is effective and complete upon patient's signature on the approved informed consent form and after the patient has been informed of participating in the study. The Investigator or study staff provides study information and the approved Informed Consent Form (ICF) to potential subjects and answers any questions during the preoperative clinic visit. In order to provide adequate time for consideration, potential subjects will take study information and ICF home with them. When an informed decision has been made (minimum consideration time 24 hours) ICFs are returned either in person or via facsimile. Any ICFs transferred via facsimile must be returned in their original version prior to surgery. A copy of the ICF will be handed over to the patient, the signed original version will be kept and traced in the patient file.

Once the patient signs the consent form, he/she is considered as enrolled in the study and will be randomized into one of the two treatment groups: ARM 1: ORIGIN PS system or ARM 2: VANGUARD PS System right after eligibility assessment about 6 to 8 weeks prior to surgery. The randomization will automatically generate a unique subject identification code which will be used through the study participation. The institution site shall keep a log of recruited subjects based on inclusion or exclusion criteria (full name, trial number, and hospital or practice identification number), in the subject identification Log.

## J. Study duration

It is anticipated that enrollment will be completed within 18 months. As each implanted subject is to be followed for two years, the estimated study duration is approximately 48 months, excluding the time required for preparing the final report. The study is considered to have ended on the date of the final visit by the final trial subject (Last patient last visit).

SYMBIOS		 symbios  Clinical Investigation Plan	F029.03
Date	27.11.2019		Distribution Informatique pdf
Auteur	BGA		
Contrôle	EBO		
Libération	RAQ		

## VIII. PROCEDURES

---

### A. Overview

Assess patient satisfaction regarding the surgery with a custom-made implant (ORIGIN®) versus off-the-shelf (VANGUARD PS) device.

Document the clinical and device performance outcomes of ORIGIN SYSTEM used in routine hospital practice in a large patient cohort for the treatment of total knee replacement (TKR).  
No additional radiological, clinical, or biological exams, compared to routine practice.

Evaluation of the performance and the safety of the ORIGIN® knee prosthesis and of the KNEE-PLAN® ORIGIN® instruments. The subjects will be treated either with the ORIGIN System or with VANGUARD PS and will be included upon eligibility assessment. Subjects will be followed at 1 and 2 years after the procedure. Study data will be recorded in the Case Report Form (Cf. APPENDICES) via an electronic platform.

### B. Investigator Site selection

The role of the principal investigator is to implement and manage the day-to-day conduct of the clinical study as well as ensure data integrity and the rights, safety and well-being of the subjects involved in the clinical study.

An investigator may be included in the clinical study if compliant with the following requirements:

- Qualified surgeon legally entitled to practice
- Experienced in the diagnosis and treatment of patients requiring a total knee replacement with ORIGIN or VANGUARD systems
- Experienced with at least 10 cumulative ORIGIN and VANGUARD implantations
- The Principal Investigator has demonstrated experience with conducting clinical (device) trials that comply with applicable regulatory standards
- Principal Investigator, co-investigators, and study staff must be willing to provide their Curriculum Vitae and training evidence

### C. Clinical Investigation Agreement

A Clinical Investigation Agreement should be in place, signed by the participating investigation site and/or principal investigator of each investigation site, as per the local legal requirements, and returned to Symbios prior to the commencement of any clinical study activities. The investigator is indicating approval of the CIP and subsequent amendments, by a fully executed agreement. The agreement is separately issued and is based on the CIP requirements.

SYMBIOS		 symbios  Clinical Investigation Plan	F029.03
Date	27.11.2019		Distribution Informatique pdf
Auteur	BGA		
Contrôle	EBO		
Libération	RAQ		

## D. EC approval

Prior to enrolling subjects in this clinical study, the local German EC will be required to approve the current Clinical Investigation Plan, the Patient Informed Consent form,. EC approval of the clinical study must be received in the form of a letter and provided to Symbios before commencement of the clinical study at an investigation site.

Competent Authorities (BfArM) submission is not required since both evaluated devices are CE marked and are being used within their indication for use.

The approval letter must contain enough information to identify the version or date of the documents approved. If this information is not contained in the approval letter, it must be retrievable from the corresponding submission letter.

## E. Study site initiation

After the EC approval is obtained, a joined Site Initiation Visit will be planned at the investigational site. A list of participating team members should be completed and maintained during the course of the Study. New personnel should only start their assignment after receiving adequate training in the clinical investigation requirements and this training shall be documented. The names, initials, signatures, functions, and designated authorizations of new personnel shall be documented.

The purpose of this visit is to provide training to the Study staff including the following items:

- Clinical Investigation Plan and execution
- Training on the device under investigation
- Training on the eCRF by the sponsor or its representative (bepatient)
- Regulatory requirements, and Investigator responsibility training provided by the sponsor or its representative (CRA TRIUM)
- Study documentations and Investigator Site File (ISF)
- Other if applicable for the correct execution of the study.

The study staff will complete a training log, to assess date of training and completion of the site initiation visit. This log will be provided by the sponsor and kept, on site, in the ISF.

## F. Description of all clinical investigation related subject procedures

### a) Preoperative data

There are established visit windows defined in this study based on standard clinical practice (Cf. XXI.APPENDICES. B. SCHEDULE OF ASSESSMENT).

During the preoperative visit, the following baseline data will be collected:

- o Subject Information or consent (at least 24h prior to the preoperative visit) – Date of consent

SYMBIOS		 symbios  Clinical Investigation Plan	F029.03
Date	27.11.2019		Distribution Informatique pdf
Auteur	BGA		
Contrôle	EBO		
Libération	RAQ		

- If consent obtained, date of preoperative visit (DD/MM/YYYY)
- Date of randomization and Arm attribution Group 1 (ORIGIN) or 2 (VANGUARD)
- Inclusion/exclusion criteria
- Demographic data:
  - Gender: Male, female
  - Year of birth, (DD/MM/YYYY)
  - Age of patient: (YY)
  - Weight, (between 20 and 250Kg)
  - Height, (between 80 and 250cm)
  - BMI (kg/m^2)
- Indication : Severe painful and/or disabled knee joint, resulting from:
  - Non-inflammatory degenerative knee joint disease
  - Osteoarthritis, necrosis, post traumatic arthritis

Or Inflammatory knee joint disease:  
Rheumatoid arthritis
- Medical Knee history
  - number of previous knee surgeries
  - description of knee surgeries: medial meniscectomy, lateral meniscectomy, arthroscopy, tibial/femoral osteotomy, other to specify
- Radiological examination
  - If patient is assigned to Arm 1: Pre-op CT Scan will be performed for the design of the ORIGIN prosthesis. Pre-op RX will be performed as well per standard of care
  - If patient is assigned to Arm 2: Pre-op RX will be performed for the implementation of the VANGUARD PS system. (AP, lateral, sunrise)
- Surgeon reported scores:
  - KSS score (Objective Knee Indicators only)
  - X-rays: AP, lateral, sunrise, long leg weight bearing film
  - Femoral patellar arthrosis (Iwano classification (stage 1 mild to 4 very severe)),
  - Knee Society Radiographic Evaluation and Scoring System (KSRESS): patellar tilt angle, patellar displacement, tibial slope, anatomical axis (angles  $\alpha - \beta$ ), mechanical axis (HKA angle, F angle, T angle, HKS angle)
  - Single Leg Stance test (SLS)
  - Timed up and go (TUG)
- Patient reported scores:
  - KOOS Score
  - OKS Score
  - FJS Score
  - EQ-5D-5L Score
  - A self-administrated patient satisfaction questionnaire.

---

 Long leg, knee in 2 planes and patella sunrise

SYMBIOS		 symbios  Clinical Investigation Plan	F029.03
Date	27.11.2019		Distribution Informatique pdf
Auteur	BGA		
Contrôle	EBO		
Libération	RAQ		

b) *Perioperative data*

1. *Surgery procedure*

The Surgery procedure is performed according to the standard procedures of the surgeon at the hospital. The surgical approach should be performed according the Instruction for Use of the ORIGIN System. Regarding VANGUARD, the operative technique is in accordance with the surgical technique guide provided by Biomet. Surgery will be performed or supervised by an experienced orthopedic surgeon.

The following data will be collected:

- Date of surgery (DD/MM/YYYY)
- Surgeon name (First and Last name)
- Implanted side (L/R)
- Approach (medial/lateral)
- Implanted device: ORIGIN PS (Monobloc or Modular) vs VANGUARD PS
- Reference & Lot number of the implanted devices if ORIGIN PS System
- Reference & Lot of the associated used instruments if ORIGIN System
- Surgery total duration time (skin-to-skin) for both Arms
- Safety evaluation for ORIGIN System & VANGUARD PS:
  - Perioperative complications
  - Perioperative difficulties
  - Surgeon satisfaction regarding devices and instruments for ORIGIN PS System (via surgeon satisfaction form)
  - Femoral and tibial sizing, patellar resurfacing
- Surgeon satisfaction: during surgery, the surgeon will assess safety and performance of the listed Instruments in the Chapter XXI.APPENDICES. These data will be collected in the case report form based on surgeon satisfaction and will be used in clinical evaluation of Symbios ORIGIN PS System.

SYMBIOS		 symbios  Clinical Investigation Plan	F029.03
Date	27.11.2019		Distribution Informatique pdf
Auteur	BGA		
Contrôle	EBO		
Libération	RAQ		

Surgeon satisfaction during surgery regarding ORIGIN IMPLANTS:

CRITERIA OF EVALUATION	SURGEON IMPLANTS SATISFACTION	
EVALUATION OF CUTTING GUIDES	 😊  😞	
	 if unsatisfied, please specify -	 Femoral cutting guide  Tibial cutting guide  Recut guide  4 in 1 guide  Intercondylar notch
COVERAGE OF FEMORAL & TIBIAL COMPONENT	 😊  😞	
	 if unsatisfied, please specify:	 Femoral component  Tibial component
TIBIAL RECUT	 Yes  No  If yes, please specify : 1mm / 2mm / 3mm / 4mm	
JOINT BALANCING	0°	 😊  😞
	30°	 😊  😞
	90°	 😊  😞
	120°	 😊  😞
PATELLA RESURFACING (if applicable)	 Yes  No	
LATERAL FACETECTOMY	 Yes  No	
LATERAL RELEASE	 Yes  No	
Modular Stem	 Yes  No If yes, please specify : 20mm / 30mm / 40mm / 70mm	
OVERALL GLOBAL SURGEON SATISFACTION	 😊  😞	

SYMBIOS		 symbios  Clinical Investigation Plan	F029.03
Date	27.11.2019		Distribution Informatique pdf
Auteur	BGA		
Contrôle	EBO		
Libération	RAQ		

Surgeon satisfaction during surgery regarding ORIGIN INSTRUMENTS

SURGICAL STEPS	INSTRUMENTS SATISFACTION
DISTAL FEMORAL CUT	 😊  😞  if unsatisfied, (Please specify name of instrument related to the comment):
A/P FEMORAL CUTS AND CHAMFER CUTS	 😊  😞  if unsatisfied, (Please specify name of instrument related to the comment):
INTERCONDYLAR CUTS	 😊  😞  if unsatisfied, (Please specify name of instrument related to the comment):
FEMUR TRIAL-EVALUATION OF THE DEFORMATION	 😊  😞  if unsatisfied, (Please specify name of instrument related to the comment):
PROXIMAL TIBIAL PRE CUT	 😊  😞  if unsatisfied, (Please specify name of instrument related to the comment):
PRE-TRIALS AND TIBIAL CUT ADJUSTMENT	 😊  😞  if unsatisfied, (Please specify name of instrument related to the comment):
TIBIAL BASE PLATE PREPARATION	 😊  😞  if unsatisfied, (Please specify name of instrument related to the comment):
FINAL TRIALS	 😊  😞  if unsatisfied, (Please specify name of instrument related to the comment):

SYMBIOS		 symbios  Clinical Investigation Plan	F029.03
Date	27.11.2019		Distribution Informatique pdf
Auteur	BGA		
Contrôle	EBO		
Libération	RAQ		

PATELLAR PREPARATION (if applicable)	 😊  😞  if unsatisfied, (Please specify name of instrument related to the comment):
IMPLANTATION	 😊  😞  if unsatisfied, (Please specify name of instrument related to the comment):

The surgeon will assess safety and performance of the listed Instruments in the Chapter XXI.APPENDICES. LIST OF INSTRUMENTS

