### B. Clinical endpoints

#### a) *Primary endpoints*

- The hypothesis regarding the scoring is that patients receiving ORIGIN implants will experience a more natural feel of the prosthesis during the first year after the surgery compared to patients receiving VANGUARD implants (as measured with FJS)
- The primary endpoint of this study is:

SYMBIOS		 symbios  Clinical Investigation Plan	F029.03
Date	27.11.2019		Distribution Informatique pdf
Auteur	BGA		
Contrôle	EBO		
Libération	RAQ		

- To compare the ability of patients to forget their operated knee at 1 year after the surgery, measured by the Forgotten Joint Score 12 (FJS-12 Knee).
- To compare patient satisfaction regarding the surgery with a CE marked custom-made implant (ORIGIN®) versus off-the-shelf (VANGUARD PS) device. A short self-reported questionnaire will be used.

*b) Secondary endpoints will evaluate clinical performance and safety of ORIGIN System:*

- **Secondary endpoints:**

- Evaluate the success of the procedure
- Evaluate surgeon satisfaction regarding the use of implants and instruments
- Evaluate outcomes: complications & revision rate with the ORIGIN SYSTEM at the last (2y) follow-up visit
- To compare the PROMs between the two groups at 1y follow-up and 2y follow-up visits.
- Evaluate performance of the ORIGIN System vs VANGUARD PS at 2 years follow-up: clinical examination and scoring.
- To evaluate/compare the clinical, functional and quality of life outcomes using the following four scores:
  - Clinical examination
  - The Knee Injury and Osteoarthritis Outcome Score (KOOS)
  - The Oxford Knee Score (OKS)
  - The EQ-5D-5L Score
  - A self-administrated patient satisfaction questionnaire.
- To evaluate/compare the clinical, functional and quality of life outcomes with the following surgeon reported scores:
  - The Knee Society Score (KSS) (Objective Knee Indicators only)
  - Knee Society Radiographic Evaluation and Scoring System (KSRESS)
  - The Single Leg Stance Test (SLS)
  - The Timed Up & Go test (TUG)
- Radiological evaluation:
  - X-rays: AP, lateral, sunrise, long leg weight bearing film
  - Femoral patellar arthrosis: Iwano classification (stage 1 mild to 4 very severe),
  - KRESS Radiological assessment: Patellar tilt angle, patellar displacement, tibial slope, anatomical axis (angles  $\alpha - \beta$ ), mechanical axis, (HKA angle, F angle, T angle, HKS angle)

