#### *d) Performance outcomes*

The device success will be evaluated via the performance assessment via the overall surgeon and patient satisfaction. Post-operative surgeon overall satisfaction will be assessed via the following answers: very

 <https://www.ncbi.nlm.nih.gov/pubmed/12719681>

Interpretation of changes in health-related quality of life: the remarkable universality of half a standard deviation

SYMBIOS		 symbios  Clinical Investigation Plan	F029.03
Date	27.11.2019		Distribution Informatique pdf
Auteur	BGA		
Contrôle	EBO		
Libération	RAQ		

satisfied, satisfied, and not satisfied. Post-operative patient satisfaction will be assessed via the FJS, with a marked improvement in the natural feel of the prosthesis during the first year after the surgery, and slightly significant improvement at the following interval of 2 years.

A final report will be prepared when all patients have completed their follow-up evaluation. No interim analysis is planned.

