### e) *Statistical Methods and Analysis*

All analyses will be described in a Statistical Analysis Plan (SAP) which will be completed prior to analysis. No interim analysis is planned.

Any deviations from this section and/or the Statistical Analysis Plan will be described and justified in the Final Clinical Study Report, as appropriate.

No statistical techniques will be used to impute missing data for continuous or categorical outcomes. If a subject's data are missing for any reason, that subject will not be included in that portion of the analysis. The number of subjects included in each analysis will be reported so that the reader can assess the potential impact of missing data.

Additional (annual) reports providing only descriptive statistics will only be written upon request of the EC/IRB and/or Regulatory Authority, as applicable.

For statistical analysis, patient satisfaction results will be analyzed into the knee awareness as:

- Never
- Almost never
- Seldom
- Sometimes
- Mostly

The subjects that required further procedures or surgeries on their knee in the initial six months were excluded from this analysis. These patients were excluded from analysis because the outcome and satisfaction scores were likely to be highly influenced by the early additional procedure, and the study was not powered to evaluate the revision rates associated with two implants.

Statistical differences could be identified in:

- Baseline demographics between ORIGIN vs VANGUARD in patient satisfaction, including slightly differences in age, comorbidities and sex.
- Surgeon overall satisfaction regarding both implants ORIGIN and VANGUARD and possible surgical factors who could play a role in the patient outcome or on the performance of the implant?
- Demonstrate superiority of ORIGIN over VANGUARD: higher score by 13.4 points based on MCID evaluation of PROMs.
- If a modular stem is used it could impact radiological analysis: radiolucencies for instance and tibial loosening

SYMBIOS		 symbios  Clinical Investigation Plan	F029.03
Date	27.11.2019		Distribution Informatique pdf
Auteur	BGA		
Contrôle	EBO		
Libération	RAQ		

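### The three-level surgeon-satisfaction result named under device success has no matching data item: the only collection described is for ORIGIN alone, during surgery, with a two-level overall rating

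*Combined protocol and SAP*

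**What the plan says.** Section X.d (Performance outcomes) states: "The device success will be evaluated via the performance assessment via the overall surgeon and patient satisfaction". It then sets the scale. "Post-operative surgeon overall satisfaction will be assessed via the following answers: very", continuing after the page break with "satisfied, satisfied, and not satisfied". That gives three levels, collected post-operatively.

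Section X.e, listing where statistical differences could be identified, includes "Surgeon overall satisfaction regarding both implants ORIGIN and VANGUARD and possible surgical factors who could play a role in the patient outcome". Section VIII.H has nearly the same item among the factors that might compromise interpretation. Section VI.B has the secondary endpoint "Evaluate surgeon satisfaction regarding the use of implants and instruments", which names no arm. The synopsis entry on collected surgical data also mentions surgeon satisfaction without an arm restriction.

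Collection is described in Section VIII.F.b. A parent bullet covers both systems, but the item below it reads "Surgeon satisfaction regarding devices and instruments for ORIGIN PS System (via surgeon satisfaction form". Two forms follow, one titled for ORIGIN implants and one for ORIGIN instruments, both to be completed during surgery. The implant form ends with "OVERALL GLOBAL SURGEON SATISFACTION", answered by ticking a happy or a sad face.

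**The concern.** The statistical section relies on a measurement that the procedures section does not produce. Three things differ: which arms are rated, how many answer levels there are, and when the rating is made.

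The surgeon's overall impression has to be recorded close to the operation. If it is not asked for VANGUARD at that time, it cannot be reliably recovered when the analysis is written. What would be lost is the three-level result for ORIGIN, and for VANGUARD any use of surgeon satisfaction, whether as an outcome or as a possible influence on patient outcome. An influence can be examined across arms only if it is measured in both.

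**Working it through.** The point rests on comparing sections. Each place in the plan that bears on surgeon satisfaction is set out below.

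| Place | Arm(s) | Answer levels | Timing |
|---|---|---|---|
| Synopsis, collected data | Not restricted | Not given | Surgery entry |
| VI.B, secondary endpoints | Not named in the item | Not given | Not given |
| VIII.F.b, data list | ORIGIN only, under a both-system bullet | Refers to the form | Surgery |
| VIII.F.b, implant form | ORIGIN only | Overall item: two | During surgery |
| VIII.F.b, instrument form | ORIGIN only | Two per step, no overall item | During surgery |
| VIII.F.c and d, 1- and 2-year lists | Absent | Absent | Absent |
| VIII.H, interpretation factors | Both | Not given | Not given |
| X.d, performance outcomes | Not stated | Three | Post-operative |
| X.e, statistical methods | Both | Not given | Not given |
| XXI.B, schedule of assessment | Absent | Absent | Absent |

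**Arms.** Only the items in VIII.F.b generate data, and all of them are limited to ORIGIN. The limit looks intended, because the neighbouring entry on operating time is marked as applying to both arms. Followed as written, VANGUARD yields 0 ratings from 70 planned procedures. ORIGIN yields at most 70, since the attempted-procedure subsection of VIII.F.b allows for patients randomised to ORIGIN who do not receive it.

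**Levels.** Three answers can be collapsed to two, but two cannot be expanded to three. If the sad face is read as not satisfied, the form still gives the proportion in the bottom category. The happy face merges the top two answers, and nothing else on the form separates them.

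**Timing.** X.d calls the rating post-operative, and the forms are headed as completed during surgery. If these are the same item, the timing conflicts. If they are different items, the three-level one is not listed anywhere for collection.

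**Does this reach the primary analysis?** The plan's sample size reproduces without any surgeon rating. The inputs are a difference of 13.4, an SD of 26.8, and z-values of 1.96 and 0.84 (Section X.a and b):

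- Effect size = 13.4 / 26.8 = 0.5.
- n = (2 / 0.5²) × (1.96 + 0.84)² = 8 × 7.84 = 62.72, rounded up to 63 per group. Power at 63 per group is 80.1%.
- Allowing for 10% loss: 63 / 0.9 = 70 per group.

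These match the plan's 63 and 70. Surgeon satisfaction enters none of these steps.

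**The case against.** The strongest reply is that ORIGIN-only collection is deliberate. Section VI.B introduces the secondary endpoints as evaluating ORIGIN. Its surgeon-satisfaction item names no comparator, although another item in that list does. VIII.F.b says the form data serve the clinical evaluation of ORIGIN, and the synopsis endpoint list omits surgeon satisfaction altogether. This stands as a defence of the detailed forms, which are legitimate device feedback. It does not supply the three-level item of X.d, and it does not fit the wording about both implants in VIII.H and X.e.

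The second reply is that the case report form is a separate document and the detailed analysis plan was still to be written, so an item not visible here may exist. That is possible, and the finding is conditional on it. Section XI.a, however, says the eCRF is built to capture the data the protocol requires, and an eCRF built to VIII.F.b would leave VANGUARD out.

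Three stronger readings are tempting, and the documents do not support them:

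- *A reader might infer that a formal between-arm comparison was promised and is now impossible.* The wording about both implants sits in lists of possible differences or influences, and the X.e bullet ends in a question mark. A comparison is implied but not committed to.
- *A reader might infer that device success cannot be computed for the control arm.* The plan never defines device success as a computed variable and never says it is required for VANGUARD.
- *A reader might infer that an uncontrolled rating of the sponsor's device would replace the randomised comparison.* Nothing says so. That comparison is the Forgotten Joint Score at 1 year.

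**Conclusion.** The inconsistency is real and worth correcting before the eCRF is fixed. As described, the plan cannot give the three-level surgeon result in X.d for ORIGIN, and it cannot give any surgeon rating for VANGUARD. In counts, that is 0 of 70 planned VANGUARD procedures rated, and the top two answers indistinguishable in up to 70 ORIGIN procedures.

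This assumes that the separate case report form matches VIII.F.b and that no further post-operative item exists outside the visit lists and schedule. The effect is confined to a secondary, descriptive item and to the surgeon part of the device-success evaluation. The primary analysis, its power and its error rate are not touched.

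**What to change.** - Record one overall surgeon-satisfaction item after every surgery in both arms, on the three-level scale of X.d. On the ORIGIN implant form it replaces the two-face overall item.
- State when it is completed, and add it to the surgical data list and the schedule of assessment.
- Reconcile the synopsis data list and Sections VI.B, VIII.F.b, VIII.H, X.d and X.e on arm, scale and timing, and check the case report form against them.
- Report the item by arm descriptively. Say that the surgeons are unblinded (Section VII.C) and that the item is not powered.
- Keep the detailed implant and instrument forms as ORIGIN-only device feedback.

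Narrowing VIII.H, X.d and X.e to an ORIGIN-only, two-level rating would also remove the contradiction, but it would give up control-arm information that costs almost nothing to collect. The cost of the recommended change is one extra eCRF question per VANGUARD procedure (70 planned) and a changed response scale on one item, with trivial surgeon time and no burden on patients.
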